supported. The app will be selected from a limited set of well-established options such as LoseIt!, MyFitnessPal, Apple Health, or Google Fit. The PGHD requested through active tracking and patient data entry will include self-monitoring elements previously shown to be successful at encouraging obesity-related behavioral change (129), such as calorie intake, food logging, minutes of physical activity, and weight. Patient contextual data requested through passive tracking may include items such as geographic location, sleep quality, and heart rate. Any additional data requested will be determined based on the results of Aim 1 and in consultation with the research team to identify social, behavioral, and clinically relevant information. Both intervention and control patients will be weighed on a clinic scale and asked to complete three PROMs pre- and post-intervention. These include the short form of the Patient Activation Measure (PAM-13), which is a validated PROM that assesses an individual's knowledge, skills and confidence in self-management behaviors (35, 36); the HRQOL-4, which is a validated PROM that assesses patients' overall physical and mental health status over the prior 30 days (37); and the Healthy Days Symptoms Module, which is a validated PROM that assesses physical and mental health symptoms which may have affected patients' lives over the prior 30 days (37). Intervention patients will also be asked to complete the three PROMs once each per month over the course of the 16-week intervention by email, online web form, text message, or app-based private message. Only privately submitted PROM data will be used in analysis, to protect patient privacy and to avoid social desirability bias due to self-curation behaviors associated with public reporting. One PROM will be collected per week, to avoid overburdening patients while ensuring a monthly collection of PROM data. The fourth week will include a simple check-in request, to maintain the weekly communication pattern. PGHD and PROs data will be extracted from shared systems, online forms, and messages as appropriate and placed into a REDCap (130) research database created for the project. These data will also be made available to and actionable by DH providers monthly through manual transfer to practice-standard patient-reported data forms and subsequent entry into the EHR. As this is a feasibility study, automated data exchange is beyond the scope of this initial project; however, the product of Specific Aim 3 will support future automated integration.

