
Outcomes and measures. The primary outcome of interest for the RCT is *patient engagement*. This outcome will be measured by patient response rates to data requests; by the frequency of unprompted messages sent by patients to research personnel; and by performance on the PAM-13. Secondary outcomes include weight loss and performance on the HRQOL-4 and Healthy Days Symptoms PROMs pre- and post-intervention. Weight loss will be assessed as change in body mass index (BMI) and absolute percent weight.

Data Analysis. Descriptive statistics will be computed for participant demographic characteristics (e.g., age, gender, race/ethnicity). Group differences (intervention vs. control) will be evaluated to ensure that the random group assignments were similar. If statistically significant differences ($p < 0.05$) are found between the groups for demographic or baseline measures, these will be controlled for in subsequent analyses. Logistic regression or the Chi-square test of proportions will be used to test differences in response rates and PROM scores between the RCT intervention and control groups. The distribution of the number of unprompted messages will be assessed and either analyzed using Poisson regression or dichotomized based on a clinically relevant cut-off and analyzed with either logistic regression or the Chi-square test of Proportions. Weight loss will be analyzed using the most appropriate and parsimonious multivariable regression technique, based on the nature of the outcome variable (e.g., continuous, time-varying, dichotomous, etc.). Fuzzy-set QCA will be conducted to examine the impact of factors identified through work conducted under Specific Aim 1.

Power. A total sample size of 256 patients is necessary to detect a proportional difference of 20% (0.55 intervention; 0.40 control) in the primary outcome between the intervention and control groups with 90% power ($\alpha = 0.05$). A sample size of 192 patients would be needed at 80% power. Given the nature of this feasibility study, we will attempt to recruit 300 patients for the RCT, but will consider the study adequately powered with 200 patients enrolled (100 intervention, 100 control). This also allows for some loss to follow-up.

3.4.3. Specific Aim 3. To create an ontology mapping and set of interoperability resources which can be used to support integration of PGHD and PROs into clinical information systems.

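### PROM scores, including the primary PAM-13, are tested only as proportions, with no cut-off and no routine baseline adjustment, which wastes power

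*Combined protocol and SAP*

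**What the plan says.** All of this is in section 3.4.2.

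- **Outcomes and measures.** The primary outcome, patient engagement, is measured in three ways: response rates, unprompted messages, "by performance on the PAM-13". HRQOL-4 and the Healthy Days Symptoms Module are secondary.
- **Data Analysis, PROMs.** "Logistic regression or the Chi-square test of proportions will be used to test differences in response rates and PROM scores" between the arms. No other method is named for a PROM, and no category, threshold or responder definition is given for one.
- **Data Analysis, other outcomes.** Message counts go to Poisson regression or may be "dichotomized based on a clinically relevant cut-off and analyzed with either logistic regression" or a Chi-square test. Weight loss gets a regression suited to the type of variable.
- **Data Analysis, baseline.** If differences significant at p<0.05 "are found between the groups for demographic or baseline measures, these will be controlled for in subsequent analyses". No other baseline adjustment is planned.
- **Methods.** Both arms are "asked to complete three PROMs pre- and post-intervention", so every patient should have a baseline score.
- **Power.** The calculation is for a difference between proportions, 0.55 v 0.40, with totals of 256 (90% power) and 192 (80% power). Enrolment of 100 per arm is accepted as enough.

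**The concern.** A response rate is a proportion; a PAM-13 score is not. Putting both under a test of proportions forces the score into categories, and differences between patients within a category are then ignored.

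Three consequences follow. First, power is lost at a sample size with little to spare. Second, the baseline score, often the best single predictor of the follow-up score, goes almost unused: a rule that adjusts only after a significant baseline difference rarely fires in a randomised trial. If the Chi-square test is chosen it cannot fire at all, since that test takes no covariates. Third, a cut-off left open until data are available makes the PAM-13 result depend on that choice, with room for false positives.

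The plan already matches method to variable for messages and weight loss, so the treatment of PROMs looks like an oversight.

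**Working it through.** **Inputs from the plan:** 0.55 v 0.40; 100 per arm (minimum) or 150 per arm (target of 300); α = 0.05, taken as two-sided. **Assumed, because the documents give nothing:** a normal score, a standardised shift d, and a pre-post correlation r of 0.3 to 0.7.

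**1. The plan's own sample sizes.** The pooled two-proportion formula is n per arm = [1.96√(2p̄(1−p̄)) + z_power√(p₁(1−p₁)+p₂(1−p₂))]² / (p₁−p₂)².

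- 0.55 v 0.40 gives 173 per arm (total 346) at 80% power and 231 (total 462) at 90%. This does not reproduce 192 and 256.
- 0.55 v 0.35 gives 96 (total 192) and 128 (total 256), an exact match.

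That mismatch is a separate point that needs reconciling. Both pairs are carried forward here.

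**2. Information kept by a split.** For a normal score cut at proportion q, relative efficiency is φ(z_q)²/[q(1−q)].

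- q = 0.50: 0.3989²/0.25 = 0.637
- q = 0.40: 0.3863²/0.24 = 0.622
- q = 0.25: 0.3178²/0.1875 = 0.539

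**3. Shift implied by the rates.** d = z(0.55) − z(0.40) = 0.126 + 0.253 = 0.379. For 0.55 v 0.35, d = 0.126 + 0.385 = 0.511.

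**4. Power at 100 per arm, d = 0.379.**

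- Split: (0.15√100 − 1.384)/0.698 = 0.166, and Φ(0.166) = 56.6%.
- Score, t-test on 198 df: noncentrality 0.379√50 = 2.68, power 76.0%.
- Score adjusted for baseline (ANCOVA), 197 df: noncentrality 2.68/√(1−r²) = 2.81, 3.09 and 3.75 for r = 0.3, 0.5 and 0.7. Power is 79.8%, 86.9% and 96.2%.

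**5. Range.**

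| n per arm | d | Split | Score | ANCOVA, r = 0.3 / 0.5 / 0.7 |
|---|---|---|---|---|
| 100 | 0.30 | 39% | 56% | 60 / 68 / 84% |
| 100 | 0.379 | 57% | 76% | 80 / 87 / 96% |
| 100 | 0.40 | 61% | 80% | 84 / 90 / 98% |
| 100 | 0.511 | 82% | 95% | 96 / 99 / >99% |
| 150 | 0.379 | 74% | 90% | 93 / 96 / >99% |

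**6. The conditional baseline rule.** Simulation: 20,000 trials per setting, 100 per arm, d = 0.379, with baseline added to the logistic model only when its between-arm p is below 0.05. Simulated split power runs slightly above the formula value in step 4.

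| Method | r = 0.3 | r = 0.5 | r = 0.7 |
|---|---|---|---|
| Split, never adjusted | 59.1% | 57.7% | 58.4% |
| Split, plan's rule | 59.1% | 58.1% | 59.5% |
| Split, always adjusted | 59.3% | 63.2% | 73.2% |
| ANCOVA on the score | 79.7% | 86.7% | 96.1% |

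The rule fired in 4.8% to 5.1% of trials and added 0 to 1 percentage point.

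**7. An open cut-off.** With no true effect, an uncorrected Chi-square test at one median cut rejected in 5.6% of 40,000 simulated trials. Taking the best of cuts at the 40th, 50th and 60th percentiles rejected in 10.5%.

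**The case against.** **Logistic regression could mean ordinal logistic regression.** That needs no binary cut. In simulation at d = 0.379 and 100 per arm, a test on the full ranks has about 73% to 74% power and four ordered groups about 68% to 70%, so much of the loss from splitting would go. But the plan never says ordinal, and the alternative it names is a test of proportions. This reading also still lacks routine baseline adjustment and stays below ANCOVA.

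**The 57% figure mixes in another problem.** This is fair. The plan does not tie 0.55 v 0.40 to PAM-13, and those rates do not yield its sample sizes. With 0.55 v 0.35 the split reaches 82%, so falling below 80% is partly a sample-size matter. The cost of splitting is then 13 points instead of 19, but it remains.

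**PROM performance might mean change from baseline.** The pre- and post-intervention wording in Outcomes and measures is attached to the secondary PROMs, not to PAM-13. Even so, a change score has relative variance 2(1−r) = 1.4, 1.0 and 0.6 at r = 0.3, 0.5 and 0.7, against 1−r² = 0.91, 0.75 and 0.51 for ANCOVA. A categorised change score would lose more.

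**The conditional rule does not invalidate the test.** Correct. Applied to a linear model it gave type I error of 5.1%, 4.4% and 3.4% at the three correlations. The fault is inefficiency. At r = 0.3 nearly all the gain comes from keeping the score.

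**Nobody proposes to pick the best of three cuts.** True. The 10.5% shows what the omission permits, and 5.6% arises with a single cut.

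**This is a feasibility pilot and PAM-13 is one measure of three.** Both true, and they limit the severity. The plan still sets out a powered comparison of the arms.

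**Conclusion.** The concern holds. As written, the plan tests PAM-13 as a proportion at an unstated cut-off and makes almost no use of a baseline score it will hold for both arms. At 100 per arm, splitting costs about 13 to 19 percentage points of power against the unadjusted score over shifts of 0.3 to 0.51 SD. Always adjusting for baseline adds a further 4 to 28 points for shifts of 0.3 to 0.4 SD, depending on r, and less at 0.51 SD, where the score alone already gives 95%.

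The direction is the same for every shift, cut and correlation tried. The size rests on assumed normality, d and r. The figures suit PAM-13 best, since HRQOL-4 and symptom items may be categories or day counts. The change should be made, but the fault does not invalidate the trial.

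**What to change.** Separate the PROM analyses from the response rates in section 3.4.2.

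- **PAM-13.** Suggested text: *Post-intervention PAM-13 score will be compared between arms by linear regression, with arm and the patient's own baseline PAM-13 score as covariates in all cases, whether or not the arms differ at baseline. The adjusted mean difference and its 95% confidence interval will be reported. Any responder cut-off will be fixed in advance and used only in a supportive analysis.*
- **HRQOL-4 and Symptoms Module.** For each item, name a linear, ordinal or count model suited to its scale before unblinded data are seen, always adjusted for that item's baseline value.
- **Binary outcomes.** Keep Chi-square or logistic regression for outcomes that are truly binary.
- **Power paragraph.** State that PAM-13 is analysed as a mean difference, and give the detectable difference at 100 per arm. By normal approximation at 80% power this is 2.80 × √(2/100) = 0.396 SD unadjusted. Multiplying by √(1−r²) gives 0.378, 0.343 or 0.283 SD at r = 0.3, 0.5 or 0.7.

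The cost is low: analysis-plan wording and one note on power. No new data, visits or patients are needed, because pre and post PROMs are already planned in both arms.

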Methods. Recruited participants will be randomized to one of two arms, intervention or control. Both intervention and control groups will engage in a 16-week program where they will receive regular health promotion messaging about (a) food, nutrition, and diet; and (b) exercise and physical activity. Existing content in these topic areas is available in a DH text messaging library aligned with the Centers for Disease Control and Prevention's (CDC) evidence-based Diabetes Prevention Program (80), for which a previous study demonstrated clinical efficacy (116). Additional messaging content will be informed by focus group and interview findings. Intervention patients will be asked to track PGHD elements related to weight management through a mobile health app loaded on their phones and/or through using a fitness tracker, depending on patient preference, and to share that information with the research team. If intervention patients do not have a fitness tracker, a low-cost COTS option will be provided for them. Both iOS and Android phone options will be

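### Response rates are repeated within patient, but the plan names only chi-square or logistic regression and sets no unit of analysis, responder cut-off or clustering term

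*Combined protocol and SAP*

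**What the plan says.** All references are to section 3.4.2 (Specific Aim 2) of the combined protocol and SAP unless stated.

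- **Outcome.** The primary outcome is patient engagement. Outcomes and measures says: "This outcome will be measured by patient response rates to data requests". The other two measures are unprompted messages and the PAM-13.
- **Schedule, intervention arm.** The programme lasts 16 weeks. "Intervention patients will also be asked to complete the three PROMs once each per month over the course of the 16-week intervention". The pace is set by "One PROM will be collected per week", and "The fourth week will include a simple check-in request, to maintain the weekly communication pattern".
- **Schedule, control arm.** Both arms complete the three questionnaires before and after the programme. Methods describes no weekly requests for controls.
- **Test.** "Logistic regression or the Chi-square test of proportions will be used to test differences in response rates and PROM scores" between the arms. A cut-off is mentioned only for the count of unprompted messages.
- **Power.** The Power paragraph compares proportions of 0.55 and 0.40 and counts patients: 256, 192, and a minimum of 200.
- **Precedent.** Section 3.3.1 reports the team's earlier text-message study as a rate per prompt (68% of prompts answered).

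**The concern.** A response rate is requests answered divided by requests sent, and one patient contributes many requests. Someone who ignores the first few is likely to ignore later ones, so the requests are correlated. A chi-square test or an ordinary logistic model needs independent observations. It can be fitted in two ways, and the plan does not choose.

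1. **Pool the requests.** The team's earlier study reported its result this way, so it is a realistic reading. The standard error is then too small and false positives exceed the stated 5%.
2. **Reduce each patient to yes or no.** The test is then valid, but the plan does not say what counts as a responder. Discarding the rest of the proportion costs power, and a cut-off chosen after seeing the data would be an open choice on a primary measure.

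**Working it through.** **1. The plan's own figure, to see which unit it implies.** Total N = 2[1.96√(2p̄q̄) + z_β√(p₁q₁ + p₂q₂)]²/(p₁ − p₂)². For 0.55 versus 0.40 at 90% power: (1.384 + 0.895)²/0.0225 = 231 per arm, 462 in total (346 at 80%). The stated 256 and 192 do not follow from the printed rates. They do follow from 0.55 versus 0.35. That is a separate problem. What matters here is the form of the calculation: two proportions, counted in patients.

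**2. Number of requests.** Intervention: 3 questionnaires × 4 months = 12, plus 4 check-ins = 16 weekly requests. Control: 3 questionnaires × 2 times = 6 forms, or 2 occasions. The plan does not define a data request, so both control counts are shown.

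**3. Pooled requests.** With equal patients per arm, m₁ and m₂ requests per patient and within-patient correlation ρ:

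- True variance is proportional to V = [1 + (m₁ − 1)ρ]/m₁ + [1 + (m₂ − 1)ρ]/m₂.
- The pooled test assumes V₀ = 1/m₁ + 1/m₂.
- Actual type I error = 2[1 − Φ(1.96/√(V/V₀))].

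Example, 16 versus 6, ρ = 0.2: V = 4/16 + 2/6 = 0.583; V₀ = 0.0625 + 0.1667 = 0.229; V/V₀ = 2.55; 1.96/√2.55 = 1.23; type I error 21.9%.

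| ρ (assumed) | 16 vs 6: V/V₀ | Type I error | 16 vs 2: V/V₀ | Type I error |
|---|---|---|---|---|
| 0.01 | 1.08 | 5.9% | 1.03 | 5.3% |
| 0.05 | 1.39 | 9.6% | 1.13 | 6.5% |
| 0.2 | 2.55 | 21.9% | 1.51 | 11.1% |
| 0.5 | 4.86 | 37.4% | 2.28 | 19.4% |

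Adding the intervention arm's own 6 pre/post forms (22 versus 6) changes little: 10.0%, 23.2% and 39.1% at ρ = 0.05, 0.2 and 0.5.

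**4. One yes/no value per patient.** Beta-binomial simulation, 100 patients per arm, 20,000 replicates, null rate 0.475, alternative 0.55 versus 0.40. It uses 16 requests in each arm, so it illustrates the cost of cutting and does not describe the control schedule. Over ρ = 0.05 to 0.5, type I error is 5.2% to 5.7% for a cut at half the requests and 4.8% to 5.1% for a t-test on the per-patient proportion.

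Relative efficiency = [(1.96 + z of power, cut)/(1.96 + z of power, proportion)]².

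| ρ | Power, proportion | Power, half cut | Relative efficiency | Loss |
|---|---|---|---|---|
| 0.2 | 98.9% | 93.6% | (3.48/4.25)² = 0.67 | 33% |
| 0.3 | 95.3% | 85.1% | (3.00/3.64)² = 0.68 | 32% |
| 0.5 | 82.9% | 70.3% | (2.49/2.91)² = 0.73 | 27% |

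**5. Requests that can be compared between arms.** Pre-intervention forms cannot reflect the intervention, and weekly requests go to one arm only. That leaves the 3 post-intervention forms. Pooling even these gives V/V₀ = 1 + 2ρ = 1.1, 1.4 and 2.0, and type I error of 6.2%, 9.8% and 16.6% at ρ = 0.05, 0.2 and 0.5.

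**The case against.** The strongest reply is that the plan never says requests will be pooled. The Power paragraph counts patients and compares two proportions, which fits one yes/no value per patient, and on that reading type I error is sound. This stands. A reader might infer from the named tests that type I error is well above 5% outright; the documents do not support that. The inflation holds only if requests are pooled, and its size depends on an assumed correlation. At ρ = 0.01, or with control requests counted as two occasions and low correlation, it is small.

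A reader might also apply 16 requests to both arms, which gives larger inflation. That is not the described design: Methods gives the weekly requests to the intervention arm only.

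Next, logistic regression can be extended to a clustered or quasi-binomial form, so the wording could accommodate a sound analysis. That is true, but nothing in the plan says so, and the chi-square alternative cannot be extended that way.

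A responder analysis is also legitimate and common, and the efficiency loss comes from an illustration. Both points are fair. They do not supply the missing responder definition.

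Finally, this is a feasibility study. But the same section plans a between-arm test at α = 0.05 with a power calculation, so the test should be well defined.

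**Conclusion.** The point holds in conditional form. The plan applies single-observation binary methods to a repeated measure without fixing the unit, the cut-off or the variance method.

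- **Pooled:** type I error of about 10% to 37% (16 versus 6 requests) or 6.5% to 19% (16 versus 2), assuming within-patient correlation of 0.05 to 0.5.
- **Yes/no per patient:** type I error near 5%, an undefined cut-off, and roughly 27% to 33% of efficiency lost at a half cut. This loss assumes 16 requests per arm and correlation of 0.2 to 0.5.

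This is more than missing detail, because neither way of applying the named tests does as well as an analysis that keeps each patient's full proportion. It is not fatal: the data needed are already planned, and it should be settled before analysis.

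**What to change.** In the Data Analysis paragraph of section 3.4.2:

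1. Name the patient as the unit of analysis and define what counts as a data request.
2. Choose one method in advance. Either analyse each patient's requests answered / requests sent by linear regression with robust variance or by quasi-binomial logistic regression, or fit a logistic GEE clustered on patient. These are not interchangeable: the linear model gives a difference in proportions and the logistic models an odds ratio, and patients are weighted differently when request counts differ.
3. Base the between-arm test on requests put to both arms after the intervention, that is, the post-intervention questionnaires. Leave the pre-intervention questionnaires out of this rate.
4. Report the intervention arm's weekly-request rate descriptively, with a patient-clustered confidence interval.
5. If a yes/no responder analysis is kept, state the cut-off in advance.

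The cost is a few sentences and a few lines of code, with no new data. The interval will be wider than under pooling. The between-arm test will also rest on only three forms per patient; if patients complete all or none of them, the proportion is close to yes/no anyway and its efficiency advantage shrinks.

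### The unprompted-message count goes to Poisson regression with unspecified standard errors or to a split at an unnumbered cut-off, chosen after its distribution is seen; no overdispersion-tolerant count analysis is named

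*Combined protocol and SAP*

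**What the plan says.** All of this is in the Combined protocol and SAP, section 3.4.2 (Specific Aim 2).

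- *Outcomes and measures*: engagement is the primary outcome. It is measured by response rates to data requests, "by the frequency of unprompted messages sent by patients to research personnel; and by performance on the PAM-13". The message measure is therefore a frequency, not any versus none.
- *Data Analysis*: the distribution of the number of messages "will be assessed and either analyzed using Poisson regression or dichotomized based on a clinically relevant cut-off"; after a split it is "analyzed with either logistic regression or the Chi-square test of Proportions".
- *Methods*: "Both intervention and control groups will engage in a 16-week program", so programme length is the same in both arms.
- *Power*: the only effect size is a proportion. The trial is sized to "detect a proportional difference of 20% (0.55 intervention; 0.40 control) in the primary outcome", and the team "will consider the study adequately powered with 200 patients enrolled (100 intervention, 100 control").

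The plan does not say what feature of the distribution sends the count to one route or the other, what number the cut-off is, whether the assessment is blind to arm, or how the Poisson standard errors are computed. Negative binomial, quasi-Poisson, robust and zero-inflated methods are not mentioned.

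**The concern.** Message counts vary more than a Poisson model allows whenever patients differ in their underlying tendency to write. That is plausible here: Aim 1 separates high from low technology users, while the trial recruits the same age and BMI range without stratifying on technology use. It remains an assumption, because the documents give no mean or variance for messages.

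If counts are overdispersed, each stated route has a weakness. Poisson regression with the usual model-based standard errors understates uncertainty, so chance differences are called significant too often. The split protects the error rate but discards the frequency that the plan set out to measure, so a real difference in message rate is missed more often than necessary. An unnumbered cut-off also leaves room to settle the threshold after the arms have been compared.

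**Working it through.** **Inputs from the plan.** 100 per arm (the minimum accepted), alpha 0.05 (taken as two-sided), count over a 16-week programme. The plan gives no figure for the message count to reproduce. Its sample sizes (256 at 90% power, 192 at 80%) are for a proportion and name no measure. For 0.55 against 0.40 the pooled two-sided formula gives 462 and 346, so they do not reproduce. That is a separate matter, and nothing below uses 256 or 192.

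**Assumed inputs.** Negative binomial counts with mean m and size k, so variance/mean = 1 + m/k; control mean 1 or 2; k = 0.5, 1 or 2; hence variance/mean 1.5 to 5. The rate effect is a ratio of 1.6.

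**Step 1: plain Poisson under no effect.** Model-based standard errors are too small by the square root of variance/mean. The false-positive rate is about 2[1 - Φ(1.96/√(variance/mean))].

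| Variance/mean | Formula | Simulated (20,000 trials) |
|---|---|---|
| 1.5 | 2[1 - Φ(1.600)] = 0.110 | 0.107 |
| 2 | 2[1 - Φ(1.386)] = 0.166 | 0.162-0.163 |
| 3 | 2[1 - Φ(1.132)] = 0.258 | 0.254-0.257 |
| 5 | 2[1 - Φ(0.877)] = 0.381 | 0.378 |

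Robust standard errors on the same model gave 0.051-0.058; negative binomial gave 0.052-0.056. With mild overdispersion (variance/mean 1.1-1.3), plain Poisson gave only 0.061-0.082.

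**Step 2: power for a rate effect, one cell by hand.** Control mean 1, intervention mean 1.6, k = 1, 100 per arm.

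- Count analysis: SE(log ratio) = √[(1/1 + 1/1 + 1/1.6 + 1/1)/100] = √0.03625 = 0.190. With ln 1.6 = 0.470, power = Φ(0.470/0.190 - 1.96) ≈ 0.69 (simulated 0.699).
- Any versus none: P(any) = m/(1 + m) = 0.500 against 0.615. The two-proportion formula gives power 0.37 (simulated 0.390).
- Three or more: 0.500³ = 0.125 against 0.615³ = 0.233, power 0.51 (best cut-off simulated 0.525).

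**Step 3: all six cells, rate ratio 1.6, simulated.**

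| Mean, variance/mean | Robust count | Best cut-off | Any vs none | Robust minus best |
|---|---|---|---|---|
| 1, 3 | 0.514 | 0.362 | 0.257 | 0.152 |
| 1, 2 | 0.699 | 0.525 | 0.390 | 0.174 |
| 1, 1.5 | 0.833 | 0.657 | 0.513 | 0.176 |
| 2, 5 | 0.578 | 0.406 | 0.213 | 0.172 |
| 2, 3 | 0.807 | 0.625 | 0.322 | 0.182 |
| 2, 2 | 0.940 | 0.810 | 0.449 | 0.130 |

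Repeat runs put the gap at 0.13-0.19. Other assumptions (control means 1, 2 and 4, variance/mean 1.5-9, rate ratio 1.5) gave a gap of 12 to 24 points. At means 0.25-0.5 it was 0.07-0.17.

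**Step 4: error after a split.** If a 5% dispersion test decided the route (the plan names none), a cut-off fixed in advance gave 3.5-5.7% false positives. That test sends 98-100% of trials to the split at means 1-2, but only 31-100% at means 0.25-0.5, where many trials would stay on Poisson. A cut-off set from the pooled distribution without arm labels (near-50% split or pooled mean) gave 4.9-5.9%. Taking the smallest p-value over thresholds ≥1 to ≥5 gave about 16-19% at means 1-2 and 6.7-15.5% at means 0.25-0.5.

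**Step 5: when the effect is not a rate shift.** If the intervention moves only the share sending any message, 0.40 to 0.55, any-versus-none has power 0.58-0.59 and the robust count 0.22-0.36.

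**The case against.** The strongest reply has four parts.

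1. *Looking at a distribution is good practice and does not break the test.* This stands. The plan speaks of the distribution of the count, not of a comparison by arm, and a pooled, arm-blind choice of cut-off keeps about 5%. A reader might infer that any cut-off settled after seeing data inflates error to 16-19%. The documents do not support that: the figure needs selection by arm result. What remains is that the plan does not exclude such selection, and that "dichotomized based on a clinically relevant cut-off" fixes no number.

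2. *The plan does not name overdispersion as the trigger, and Poisson regression does not rule out robust standard errors.* Also correct. A reader might infer that the trial will run at 11-38% false positives, or must dichotomise once overdispersion is seen. Neither follows: the first needs model-based errors used despite overdispersion, and the second is read from silence. The gap is that the text settles neither question.

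3. *The count analysis can lose more than it gains.* True if only the decision to write at all is affected: a loss of 0.22-0.37, against a gain of 0.13-0.19 under a rate effect. The documents do not say which effect is expected, and the sole planned effect is a proportion. Against that, the measure is defined as "by the frequency of unprompted messages sent by patients to research personnel", which favours the count as primary with a split beside it.

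4. *This is one of three measures in a feasibility study.* That limits the weight of the point. The plan nevertheless states a hypothesis of improved engagement, sets alpha and power, and tests between arms.

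**Conclusion.** The gap in the text needs no assumption: a primary-outcome measure has two possible analyses, chosen after inspection, with no criterion, cut-off number or standard-error method and no overdispersion-tolerant count analysis named. It should be closed, but it does not invalidate the trial.

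The size rests wholly on assumed counts. With negative binomial counts of mean 1-2, variance/mean 1.5-5 and 100 per arm, plain Poisson gives about 11-38% false positives against 5-6% robust. A pre-fixed split is valid at about 5% but gives up about 0.13-0.19 of power at a rate ratio of 1.6. In the rate-effect scenarios run with overdispersed counts, the robust count had more power than the best split; the size varied, and with mild overdispersion the excess error was small. The preference for the count reverses if the intervention changes only whether a patient writes. Confidence is medium, because no message rate or variance is available.

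**What to change.** In section 3.4.2, Data Analysis, replace the sentence on unprompted messages with one pre-specified analysis: Poisson regression of each patient's message count on arm with robust (sandwich) standard errors, reporting the rate ratio and 95% CI. State any cut-off as a number before arm-level data are seen, and report the dichotomy as a secondary analysis. Remove the choice of route after inspection. Whether to use an offset for observation time is left open here: programme length is fixed, but the plan expects some loss to follow-up, and arguments run both ways.

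The cost is wording only, with no new data. If counts are truly Poisson, essentially nothing is lost: at a rate ratio of 1.4 and means 0.5, 1 and 2, power is 0.44, 0.73 and 0.96 with either kind of standard error. Under the assumed overdispersion, intervals on the log scale are about 1.2-2.4 times as wide as plain Poisson would report. The real downside is the lower power when the effect is only on sending any message, which is why the pre-fixed dichotomy is kept.
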